### **Other significant Adverse Events**

An expert will identify other significant Adverse Events (OAEs) during the evaluation of safety data for the Clinical Study Report. Significant adverse events of particular clinical importance, other than SAEs and those AEs leading to discontinuation of the subject from study treatment, will be classified as OAEs. Examples of these are marked haematological and other laboratory abnormalities, and certain events that lead to intervention (other than those already classified as serious), dose reduction or significant additional treatment. For each OAE, a narrative will be written and included in the Clinical Study Report.

### **Overdose**

- An overdose with associated AEs is recorded as the AE diagnosis/symptoms on the relevant AE modules in the CRF.

Clinical Study Protocol  
Study Code: MiLe-1  
Drug Substance: Levosimendan  
EudraCT No: 013-003105-25  
Date

## **Appendix D- Ethics and regulatory review**

---

The final study protocol, including the final version of the Written Informed Consent Form and other information given to subjects eg, advertisements must be approved or given a favourable opinion by an Ethics Committee before enrolment of any subject into the study.

Before enrolment of any subject into the study, the final study protocol, including the final version of the Informed Consent Form, is approved by the national regulatory authority or a notification to the national regulatory authority is done, according to local regulations.

It is the responsibility of the Principal Investigator to apply to the Ethics Committee in writing. The application document should:

- contain the name and address of the Ethics Committee
- clearly identify, by title and date, the protocol and other documents submitted for review
- be dated.

In addition, the Principal Investigator should request the Ethics Committee to provide:

- their approval/opinion in a dated document identifying the Principal Investigator's application
- Ethics Committee composition for the meeting when the approval was given
- a statement confirming that the Ethics Committee is organised and operates according to GCP and applicable laws and regulations.

The Principal Investigator is responsible for informing the Ethics Committee of any modifications and amendments to the protocol as per local requirements.

Progress reports and notifications of serious and unexpected adverse drug reactions will be provided to the Ethics Committee according to local regulations and guidelines

All correspondence with the Ethics Committee should be filed by the Principal Investigator in the ISF.

The Principle Investigator is also responsible for obtaining approvals from scientific bodies (eg, to use radiolabelled substances) if necessary for the study.

## **SUBJECT INFORMATION AND WRITTEN INFORMED CONSENT FORM**

The Principal Investigator(s) at each centre will ensure that the subject is given full and adequate oral and written information about the nature, purpose, possible risk and benefit of the study. Subjects must also be notified that they are free to discontinue from the study at any time. The subject should be given the opportunity to ask questions and allowed time to consider the information provided.

The subject's signed and dated informed consent must be obtained before conducting any procedure specifically for the study.

The Principal Investigator(s) must store the original, signed Informed Consent Form in the Investigator's Study File. A copy of the signed Informed Consent Form must be given to the subject.

If a protocol amendment requires a change to the Informed Consent Form, the Ethics Committee must approve modifications that lead to a revised Informed Consent Form before the revised form is used.

## **SUBJECT DATA PROTECTION**

The Informed Consent Form will incorporate (or, in some cases, be accompanied by a separate document incorporating) wording that complies with relevant data protection and privacy legislation.

Extra precautions are taken to preserve confidentiality and prevent genetic or other study data being linked to the identity of the subject. In exceptional circumstances, however, certain individuals might see both the genetic, other study data and the personal identifiers of a subject. For example, in the case of a medical emergency or an investigator might know a subject's identity and also have access to his or her data. Also Regulatory authorities may require access to the relevant files, though the subject's medical information and the genetic files would remain physically separate

## **AUDITS AND INSPECTIONS**

Authorized representatives of Sponsor, a regulatory authority, or an Ethics Committee may perform audits or inspections at the centre, including source data verification. The purpose of an audit or inspection is to systematically and independently examine all study-related activities and documents, to determine whether these activities were conducted, and data were recorded, analysed, and accurately reported according to the protocol, Good Clinical Practice

Clinical Study Protocol

Study Code: MiLe-1

Drug Substance: Levosimendan

EudraCT No: 013-003105-25

Date

(GCP), guidelines of the International Conference on Harmonisation (ICH), and any applicable regulatory requirements.

**Section of protocol to be amended:**

Table 1 in Section 3 of the Study Protocol

---

Previous text	Revised text
No previous text	New activities in Table 1: Pharmacokinetics 6 hours, 24 hours, 48 hours and 4,5 days
	Routine echocardiography (pre-op, after CPB termination, first post-op day and at discharge) and 30 days post-op

---

**Reason for Amendment:**

Pharmacokinetics at 4/5 days: For a more complete analyse of the time course of drug absorption, distribution, metabolism and excretion.

Echocardiography at day 30: For extended safety surveillance

There will be no negative consequences for the patients rather opposite, it will increase patients' safety and give a better interpretation of the PK

**Actions to be taken:**

Table 1 in Study Protocol will be revised

**Section of protocol to be amended:**

Exclusion criteria in Protocol Synopsis and in Section 4-2 of the Study Protocol

---

Previous text	Revised text
Use of nephrotoxic drugs (like ibuprofen, angiotensin-converting-enzyme inhibitors, gentamicin, vancomycin) preoperative or postoperative until first postoperative until first post operative day	7. Use of nephrotoxic drugs (like ibuprofen, gentamicin, vancomycin) preoperative or postoperative until first postoperative until first post operative day

---

**Reason for Amendment:**

We have included the Ross score in to the protocol after an agreement with our pediatric cardiologist. Ross score grades the patients according to the severity of their heart failure.

According the same agreement with pediatric cardiologist peers there will be no negative consequences for the patients rather the opposite; the study will include those patients who receive angiotensin-converting-enzyme inhibitors for their heart failure.

Actions to be taken:

Change of the exclusion criteria text

**Reason for Amendment:**

The study logistics necessitates involving of a research assistant.

**Actions to be taken:**

Adding the revised text to the section Collaborators in the Study Protocol.

**Amendment: Definition of adverse events (AE) in MiLe-1**

**Reason for Amendment:**

Lack of definition of AEs, in contrast to SAEs which were well-defined.

**Actions to be taken:**

AEs, according to following criteria, for all included patients will separately be registered.

AEs Criteria:

1. Heart rate > 200/min at these time points: 2, 6, 10-12 hours after CPB weaning, first postop morning at 6 o'clock and 24 hours after CPB weaning [1]
2. Arrhythmias (rhythm other than sinusrythm). Same time points as in no 1 [2,3]
3. Inotropic score > 20 at the same time points as in no 1 [4]
4. Thrombocytes < 50.000 on the first postoperative morning [3]
5. Hypokalemia < 3.5 at the same time points as in no 1 [2]

References:

- 1) Advanced Paediatric Life Support (APLS)
- 2) Pharmaceutical Specialities in Sweden (Farmaceutiska Specialiteter i Sverige: Fass)
- 3) Hoffman TM. Cirkulation 2003;107:996-1002
- 4) Gaies MG. Pediatr Crit Care Med 2010; 234-238

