### **3.1.1 Stopping criteria for dose change**

General stopping criteria are hypersensitivity reactions to the active substance or any recipients.

The children are thoroughly monitored during surgery and postoperatively as per routine at the clinic including continuous blood pressure, pulse, and ECG monitoring. It should be noted that the initiation of Levosimendan/Milrinone occurs during the cardiopulmonary bypass time where cardiopulmonary function parameters (like blood pressure) are optimized before the termination of cardiopulmonary bypass.

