**Table 3 Adverse events dependent on the disease or surgical treatment postoperatively**

	Occurrence	Treatable	Usual Length of episodes	Prophylactic Measures	Watchfulness and Preparedness for initiation of treatment	Careful monitoring
Hypotension episodes	Usual	Yes	Minutes	Taken routinely	Present	Present
Arrhythmias episodes	Usual	Yes	Minutes to hours	Taken routinely	Present	Present

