4.4.2 Secondary endpoints post-op

Post-op will be measured at 5-10 min before CBP (T0), 5-10 min after CBP (T1), 2h after weaning from CPB (T2), 6h after weaning from CPB (T3), 8-12 hours post CBP-weaning, 24h after weaning from CPB (T4), 4 days after weaning from CPB (T5) (all variables are not

STATISTISKA KONSULTGRUPPEN		Statistical Analysis Plan	
Protocol: The prophylactic effect of Levosimendan in reducing acute kidney injury postoperatively in pediatric patients undergoing corrective heart surgery	Protocol No: MiLe-1	Version: 1.0	Page 11 of 17

present at all timepoints). Changes from T0 will be calculated for all variables where applicable.

Hemodynamic parameters measured at T0-T4 (not T5) and additionally at 8-12 hours post CPB-weaning

- Heart rate (BPM)
- Heart rhythm (SR/NR/Other)
- Pacing (Yes/No) (Missing on T0)
- Mean BP M A P (mmHg)
- CVP (mmHg)
- Central venous saturation (%)
- NIRS brain (%)
- NIRS kidney (%)
- Ventilated (Yes/No)

Arterial blood gas test

- pH
- sO₂ (%)
- cLac (mmol/L)
- Hb (g/L)
- Hct

Rate of vasoactive drugs

- Inotropic score
- 2 ml blood sample in ice taken (YES/NO)

NGAL

- NGAL plasma

T5

- T5 taken at postoperative day nr (2-7)

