4.5 Safety Variables

4.5.1 Adverse Events

Adverse Event within 28 days from surgery. AEs are collected in the following 5 categories at CRF page Adverse Events:

- Heart rate > 200/min at these time points: 2, 6, 10-12 hours after CPB-weaning, first postop morning at 6 am, 24 hours after CPB-weaning

STATISTISKA KONSULTGRUPPEN		Statistical Analysis Plan	
Protocol: The prophylactic effect of Levosimendan in reducing acute kidney injury postoperatively in pediatric patients undergoing corrective heart surgery	Protocol No: MiLe-1	Version: 1.0	Page 14 of 17

- Arrytmias at same time points as for heart rate >200/minInotropic score > 20 at same time points as for heart rate >200/minThrombocytes < 50 10⁹/L on the first postoperative morning
- Hypokalemia < 3.5 mmol/L at same time points as for heart rate >200/min

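### Arrhythmia adverse events are counted from five spot readings in 24 hours, so the SAP's counts are point prevalence and miss most episodes shorter than about 2.5 hours

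*Protocol*

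**What the plan says.** The protocol amendment on the definition of adverse events lists five criteria. The first, heart rate above 200/min, is read "at these time points: 2, 6, 10-12 hours after CPB weaning, first postop morning at 6 o'clock and 24 hours after CPB weaning". The second is "Arrhythmias (rhythm other than sinusrythm). Same time points as in no 1 [2,3". SAP 4.5.1 takes this over: "AEs are collected in the following 5 categories at CRF page Adverse Events", with "Heart rate > 200/min at these time points: 2, 6, 10-12 hours after CPB-weaning" and the remaining times as in the amendment, and arrhythmia at those same times. The SAP's stated window is much longer, "Adverse Event within 28 days from surgery", but for these two criteria the last reading is at 24 hours.

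Protocol Table 3 gives the usual length of arrhythmia episodes as "Minutes to hours". Protocol 3.1.1 describes routine monitoring "including continuous blood pressure, pulse, and ECG monitoring", and Table 1 lists continuous ECG monitoring as a study activity. Protocol Section 3 (text after Figure 2) and 6.1 place arrhythmias that need treatment in the CRF. Appendix C says that AEs found by observation are also recorded there.

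The SAP records rhythm separately as a secondary variable: "Hemodynamic parameters measured at T0-T4 (not T5) and additionally at 8-12 hours post CPB-weaning".

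**The concern.** A spot reading shows the rhythm at that moment. It does not show whether an arrhythmia occurred since the previous reading. If episodes are short compared with the gaps between readings, a count built from readings understates how many children had an arrhythmia.

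This matters because Protocol 7.1.4 names arrhythmia as an adverse reaction of both study drugs. Tables 14.5.1-14.5.3 are where a reader will look for it, under titles that suggest all AEs. A treated but non-serious arrhythmia at hour 4 belongs in the CRF under Protocol 6.1, yet it has no stated path into those tables.

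**Working it through.** The documents state no detection rate or expected arrhythmia rate, so there is no figure of theirs to reproduce. The check asks what share of episodes five readings can see.

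**Inputs from the documents.** Readings at 2, 6, 10-12 and 24 hours after weaning, and at 06:00 (AE amendment, SAP 4.5.1). Episode length of minutes to hours (Table 3).

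**Assumptions.** One episode per child, onset uniform over 0-24 hours after weaning, fixed duration d. In the base case weaning is at 14:00, so 06:00 falls at 16 hours, and the middle reading is at 11 hours. Readings are then at 2, 6, 11, 16 and 24 hours, with gaps of 2, 4, 5, 5 and 8 hours. The range covers weaning on the hour from 11:00 to 18:00 and a middle reading at 10, 11 or 12 hours.

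**Formula.** An episode is caught if at least one reading falls inside it:

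P(caught) = [sum over gaps of min(d, gap)] / 24

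For d up to 2 hours the base case reduces to 5d/24.

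| Duration d | Sum of min(d, gap), h | Caught (base) | Missed (base) | Missed (range) |
|---|---|---|---|---|
| 5 min | 0.42 | 1.7% | 98% | 98-99% |
| 30 min | 2.5 | 10% | 90% | 90-92% |
| 1 h | 5 | 21% | 79% | 79-83% |
| 2 h | 10 | 42% | 58% | 58-67% |
| 2.5 h | 12 | 50% | 50% | 50-60% |
| 3 h | 14 | 58% | 42% | 42-54% |
| 4 h | 18 | 75% | 25% | 25-42% |
| 6 h | 22 | 92% | 8% | 0-25% |
| 8 h | 24 | 100% | 0% | 0-17% |

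**Break-even.** For d between 2 and 4 hours the base case gives (2 + 4d)/24 = 0.5, so d = 2.5 h. The least favourable schedule has weaning at 18:00 and the middle reading at 12 hours, which coincides with 06:00. The gaps are then 2, 4, 6 and 12 hours, and (2 + 3d)/24 = 0.5 gives d = 3.3 h.

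**Mixed durations (assumed, base schedule).** The share caught is 20% for exponential durations with mean 1 h, 47% with mean 3 h and 55% with mean 4 h. It is 27% for log-uniform durations from 5 min to 6 h, and 56% for uniform durations over the same span. The overall share missed therefore runs from 80% to 44% across these choices.

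**Repeated episodes.** A child with three independent 1-hour episodes is flagged with probability 1 - (1 - 0.208)^3 = 50%.

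**Comparison of arms.** If true incidences are a and b and each event is detected with the same probability p, the observed rates are pa and pb. The ratio is still a/b. The difference shrinks to p(a - b), and fewer events are counted.

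**The case against.** Fixed, identical readings under blinding are a legitimate way to ascertain events, and several objections have force.

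- A reader might infer that most arrhythmia episodes are missed. The documents do not support that. Table 3 gives no distribution and no upper limit, and at the longer end of its range most episodes are caught (75% at 4 hours, base case).
- A reader might extend the result to heart rate above 200/min. Table 3 covers only hypotension and arrhythmias, so the documents give no duration for tachycardia.
- A reader might infer that the arms are pulled together on the ratio scale. With equal detection they are not. Unequal detection would need arm-specific durations or episode counts, which are not given. Nor is a planned test weakened: Protocol 10.2 and SAP 5.6.1 make safety descriptive.
- The amendment registers its list separately and does not say that it replaces the general AE definition. Serious events have their own route. The SAP also tabulates Cordarone and beta-blocker use by ICU day (4.2.2), and rhythm and pacing at set times and each morning (4.4.2, 4.4.3). These are partial views of the same events. They do not close the gap, because drug use does not identify an arrhythmia and the rhythm records are themselves spot readings.
- A reader might want every episode on the continuous ECG scored from the start of infusion. That is debatable. Infusion starts on bypass, Protocol 7.1.15 says many children are paced routinely, and no annotated continuous record is described.
- The mismatch between 10-12 and 8-12 hours costs data only if the AE page is filled from the haemodynamic record. The documents do not say that it is.

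What stands is that SAP 4.5.1 names only the five categories as the AE data and does not list treatment-needing arrhythmia among them. Protocol 7.1.9 may also close the general route for heart rate, since it admits vital-sign deterioration as an AE only if it is serious or leads to discontinuation.

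**Conclusion.** The point holds in a bounded form. Followed as written, SAP 4.5.1 yields arrhythmia counts that are point prevalence at five fixed times, shown in tables that will be read as occurrence. For single episodes with uniform onset, the readings miss about 90% at 30 minutes, 79% at 1 hour and 58% at 2 hours. The balance turns at about 2.5 hours (up to 3.3 hours under the least favourable schedule).

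The overall shortfall cannot be stated, because it depends on durations and on episodes per child that the documents do not give. The consequence is lower absolute rates and less precision. Bias in the risk ratio is not shown. The primary analysis is unaffected.

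**What to change.** 1. Add treatment-needing arrhythmia to SAP 4.5.1 and to Tables 14.5.1-14.5.3, as n (%) of subjects by arm over the protocol's AE period (7.1.8: randomisation to five days after the start of infusion, plus day 30). State that AEs observed between readings and recorded under Appendix C also enter those tables. Confirm that the CRF item covers the infusion period, since Section 3 introduces it among the follow-up parameters.
2. Keep the five spot readings, but label them as point prevalence at fixed times.
3. Reconcile the 10-12 hour AE reading (amendment, SAP 4.5.1) with the 8-12 hour haemodynamic record (SAP 4.4.2), and say whether one record serves both.

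The cost is SAP wording, an added variable and table rows, and some data extraction if the item was not entered in the database. Reported event counts will be higher. Treated arrhythmia also depends partly on each clinician's threshold for treating, although caregivers are blinded.

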1 STUDY DETAILS

1.1 Study Objectives

The aim of the study is to assess the ability of Levosimendan to reduce the postoperative acute kidney injury in pediatric patients undergoing surgery for congenital heart disease (CHDs).

The primary objective of this study is to investigate the preventive effect of Levosimendan on postoperative acute kidney injury in pediatric patients undergoing surgery for their CHDs. Creatinine at the second postoperative day will be the primary endpoint.

1.2 Study Design

This is a parallel-group, prospective, randomized, double-blinded controlled study in pediatric patients in need for surgery due to their CHD.

A total of 70 infants will be included in the study and undergo open heart surgery according to routine procedures at the two participating hospitals. Patients will be randomly assigned to receive either Levosimendan (test group) or Milrinone (control group). Serum creatinine, the common marker of acute kidney injury, will be measured daily according to the clinical routines. The length of treatment (Levosimendan or Milrinone) is 26 hours. The treatment will be started during the operation at the same time-point at which Milrinone infusion routinely is started. Blood samples will be obtained at five occasions, during 24 hours perioperatively. Patients will be followed for at least 48 hours after termination of the treatment, including hemodynamic monitoring, blood gases, serum creatinine. Furthermore, there is a follow-up for possible adverse events/serious adverse events for 28 days from the surgery (phone call to parents and/or to the local hospital).

STATISTISKA KONSULTGRUPPEN	Statistical Analysis Plan
Protocol: The prophylactic effect of Levosimendan in reducing acute kidney injury postoperatively in pediatric patients undergoing corrective heart surgery	Protocol No: MiLe-1 Version: 1.0 Page 5 of 17

Figure 1 *Study design*

[figure not shown]

Figure 2 Study flow chart

[figure not shown]

Table 1 Study activities

STATISTISKA KONSULTGRUPPEN										Statistical Analysis Plan	
Protocol:									Protocol No:		
The prophylactic effect of Levosimendan in reducing acute kidney injury postoperatively in pediatric patients undergoing corrective heart surgery								MiLe-1	Version:		
								1.0	Page 6 of 17		

Weight, height	X										
Medical history	X										
Physical examination	X										
Inclusion/exclusion criteria	X										
Randomization	X										
Surgery		X									
Levosimendan/ Milrinone		X	X	X	X	X					
Pulse, Blood pressure, CVP, blood gases		X	X	X	X	X					
Blood for laboratory screen		X									
Serum Hb, WBC, CRP Albumin, Creatinine, Urea, CystatinC		X						X			
Volume status, diuresis, weight								X			
Pulse, BP								X			
Study specific blood		X	X	X	X	X			X		
Continuous ECG monitoring		X	X	X	X	X					
Continuous hemodynamic and respiratory monitoring		X	X	X	X	X					
Serious Adverse event and Adverse event recording		X	X	X	X	X		X	X	X	

1.3 Treatment Groups

Active: Levosimendan 2.5 mg/mL solution, diluted to 0.05 mg/mL i.v.

Control: Milrinone i.v. standard of care

1.4 Sample Size

The number of patients needed for the study is based on a 20% reduction in serum creatinine in the Levosimendan group compared with the Milrinone group in the day after stopping the infusion of Levosimendan/Milrinone (second postoperative day). The power of study is set on 80 %.

The study will contain two groups; Levosimendan (n=35) and Milrinone n=35). Patients in the Levosimendan group will receive Levosimendan as inotrope agent and patients in the

STATISTISKA KONSULTGRUPPEN		Statistical Analysis Plan	
Protocol: The prophylactic effect of Levosimendan in reducing acute kidney injury postoperatively in pediatric patients undergoing corrective heart surgery		Protocol No: MiLe-1	Version: 1.0 Page 7 of 17

Milrinone group will receive Milrinone as inotrope agent. Patients will randomly be assigned to either group. The caregivers (physicians, nurses and nurse-assistants) and the investigators will be blinded for the study drug. The same infusion rate and total volume of Levosimendan and Milrinone will be applied to both groups.

2 STUDY DATA

Analyses regarding inflammatory and brain injury biomarkers, pharmacokinetics and echocardiography will not be presented in this analysis plan. Separate analysis plans will be written for these data.

